4 INTRODUCTION

Osteoarthritis (OA) is the most prevalent joint disorder worldwide and is associated with significant pain and disability [1]. It is a progressive disease that can affect any joint, but most often involves the weight bearing joints such as the knee. The European Project on Osteoarthritis reported on prevalence rates for knee OA in Europe and the United Kingdom (UK). For subjects aged 65-74 years, the rate of knee OA based on clinical judgment was 36.7% in Italy and 18.6 % in the UK. For subjects aged 75 years or older the rate, based on clinical judgment was 50.8% in Italy. In the Netherlands, the self-reported rate of knee OA in subjects 65-74 years was 23.6% and for subjects 75 years or older was 31.4% [2]. Because of the high prevalence of knee OA, this disease ranked as either the top or second leading cause of disability [3]. In particular, this disease accounted for more dependence on others in climbing stairs, housekeeping and walking a mile than any other disease after adjustment for age, sex and comorbidity [3].

Osteoarthritis is defined as a “heterogenous group of conditions that leads to joint symptoms and signs which are associated with defective integrity of articular cartilage in addition to related changes in the underlying bone and at the joint margins” [4]. OA is characterized by a decreased concentration of HA in synovial fluid and a slow degradation of cartilage over years [5, 6]. The decreased concentration of HA in the synovial fluid of an osteoarthritic joint is probably caused by dilution from exudation, a decreased production of hyaluronans, and increased degradation [6]. Accordingly, the average molecular weight is diminished resulting in a loss of the viscoelastic properties of the synovial fluid for which HA is responsible [5].

Corticosteroids have long been used to alleviate pain and inflammation by injecting into the intra-articular space. Commonly used corticosteroids have been triamcinolone acetonide (TA) and triamcinolone hexacetonide (TH), which have been reviewed in the literature and found to be safe and effective for short term relief of the symptoms of osteoarthritis.[7] Standard dosing for intra-articular injections to the knee for triamcinolone hexacetonide (TH) have been reported as a 1 ml injection at a concentration of 20 mg/ml, which will be the proposed dose for the active control in this trial.[7]

Viscosupplements are believed to restore the concentration of hyaluronans in synovial fluid, elevate the viscosity and improve the lubricating and cushioning properties of the synovial fluid to a healthier state to alleviate pain in OA [6]. HA in synovial fluid binds to chondrocytes, supporting a role for HA in healthy cartilage [5]. HA has been studied as a substance capable of restoring the normal properties of synovial fluid and cartilage, thereby reducing pain and stiffness in the osteoarthritic joints.

Exogenously administered HA immediately restores the synovial fluid's viscoelastic (or rheologic) properties [6].

Bellamy et al (2006) conducted a systematic analysis of 76 single and double-blinded studies and concluded that viscosupplements are an effective treatment for OA of the knee with beneficial effects on pain, function and Patient Global Assessment from a 5 to 13 week post injection period showing a percent improvement from baseline of 28% to 54% for pain and 9% to 32% for function [8].

Because data show a delayed treatment effect of HA, Anika Therapeutics wanted to create a product (Cingal) that could provide quicker pain relief for subjects suffering from osteoarthritis while still providing the established pain relief of an HA product.

Cingal is a sterile, biocompatible, non-pyrogenic, viscoelastic, uniform white/off white opaque solution composed of molecules of HA and triamcinolone hexacetonide (TH). Cingal is indicated in the treatment on pain in osteoarthritis (OA) of the knee in patients who have failed to respond to conservative non-pharmacological therapy and to simple analgesics, e.g., acetaminophen. Cingal functions as a viscoelastic supplement or a replacement for synovial fluid in human joints with short term pain relief is provided by triamcinolone hexacetonide. This clinical trial will evaluate the efficacy and safety of a single injection of Cingal for relief of joint pain in subjects with OA of the knee who have not responded to conservative treatment.

Anika Therapeutics, Inc are currently conducting the Cingal 16-02 study, which is a randomized, double-blind, active- controlled, multi-center study of a single injection of cross-linked sodium hyaluronate combined with triamcinolone hexacetonide (Cingal[®]) to provide symptomatic relief of osteoarthritis of the knee. Enrollment of 576 patients at up to 30 sites is being completed in a randomization of 4:4:1 (Cingal, Monovisc: triamcinolone hexacetonide). Subjects are currently in the enrollment or follow up stage of the Cingal 16-02 trial. The purpose of the Cingal 17-02 sub-study will be to evaluate the efficacy and safety of the treatment at 39 weeks post treatment.

6 STUDY OBJECTIVES

The objective of this sub-study is to evaluate the efficacy and safety at 39 week follow up of a single injection of Cingal for relief of joint pain in subjects with OA of the knee who have not responded to conservative treatment (weight reduction, physical therapy, pain medications, etc.).

7 ENDPOINTS

7.1 Primary Efficacy Endpoint

- The responder rate as identified by the Outcomes Measures for Rheumatic Arthritis Clinical Trials-Osteoarthritis Research Society International (OMERACT-OARSI) responder index at 39 weeks post treatment comparing the Cingal group to the TH group.

7.2 Secondary Efficacy Endpoints

- The change from baseline in knee pain as measured by the WOMAC Pain Score (100 mm VAS) at 39 weeks post treatment comparing the Cingal group to the TH group.
- The change from baseline in WOMAC Physical Function score at 39 weeks post treatment comparing the Cingal group to the TH group.
- The change from baseline in WOMAC Stiffness score at 39 weeks post treatment comparing the Cingal group to the TH group.
- The change from baseline in Total WOMAC score at 39 weeks post treatment comparing the Cingal group to the TH group.
- The change from baseline in the Patient Global Assessment 39 weeks post treatment in the Cingal group compared to the TH group.
- The change from baseline in the Evaluator Global Assessment at 39 weeks post treatment in the Cingal group compared to the TH group.
- The usage of rescue medication through 39 weeks post treatment in the Cingal group compared to the TH group.

7.3 Exploratory Endpoints

Any comparisons between groups (Cingal, Monovisc, TH), within groups and / or time points (from baseline through to 39 weeks) not described in the primary or secondary endpoints may be presented in the exploratory endpoints including:

[figure not shown]
- EuroQol (EQ-5D)
- WOMAC Pain Score (100mm VAS)
- OMERACT-OARSI
- Total WOMAC
- WOMAC Stiffness Score
- WOMAC Physical Function
- Patient Global Assessment
- Evaluator Global Assessment
- Range of Motion
- Rescue Medication Usage
- Number of Treatment Failures due to Additional Procedure or Use of Disallowed Medication

7.4 Safety Endpoint:

The incidence, timing, severity, and relationship to treatment of all Adverse Events (AE) will be collected and coded using Medical Dictionary for Regulatory Activities (MedDRA). Local injection site and non-local events will be recorded separately.

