3 STUDY SYNOPSIS

Title	Extension Study to Cingal 16-02: Trial Extension to 39 Week Follow Up in the Randomized, Double-Blind, Active Comparator Controlled, Multi-Center Study of a Single Injection Cross-Linked Sodium Hyaluronate Combined with Triamcinolone Hexacetonide (Cingal) to Provide Symptomatic Relief of Osteoarthritis of the Knee
Study Objective	To evaluate the efficacy and safety of a single injection of Cingal for relief of joint pain at 39 week follow up in subjects with Osteoarthritis (OA) of the knee who have not responded to conservative treatment.
Investigational Product	Subjects enrolled in Cingal 17-02 will not receive an injection. For reference only, the investigational product utilized in Cingal 16-02 was: Cingal : A chemically cross-linked sodium hyaluronate supplied as a 4-mL unit dose with a nominal 18 mg of triamcinolone hexacetonide (TH) in a 5-mL glass syringe.
Comparator Product	Subjects enrolled in Cingal 17-02 will not receive an injection. For reference only, the comparator products utilized in Cingal 16-02 were: Triamcinolone Hexacetonide (TH) : 20 mg/ml supplied as 1 mL unit dose in a glass ampoule. Monovisc® : A chemically cross-linked sodium hyaluronate supplied as a 4-mL unit dose in a 5-mL glass syringe.
Mode of Delivery	For reference only, the mode of delivery in Cingal 16-02 was: Cingal, Triamcinolone Hexacetonide, or Monovisc will be injected into the intraarticular (IA) space of the index knee using an 18-21 gauge needle.
Study Design	Multi-center, randomized, double-blind, parallel group, 3-arm, active comparator controlled study
Phase	Phase III
Sample Size	A total of 576 subjects will be enrolled. This equates to 256 subjects injected with Cingal, 256 subjects injected with Monovisc and 64 subjects injected with TH. All subjects who meet enrollment criteria and completed the 26 week follow up in Cingal 16-02 will have the option to participate in the sub-study.
Study Duration	The entire sub-study duration will be an additional 13 weeks. The follow up visit will be scheduled at 39 weeks post treatment.

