10.2.12.3 Concomitant Medications

A medication is considered concomitant if taken after signing the ICF and up to and including the 39 week follow-up visit. Data on medications will include: medication name, dose, unit, route, frequency, start date, stop date, indication and whether the medication was taken for an AE.

At each study visit, the subject will be asked about any new medications that were started since the last visit. Indications for any new medications during the study period will be recorded as AEs, unless the medications are administered for a pre-existing condition.

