12.1.3 Exploratory Endpoints

Any comparisons between groups (Cingal, Monovisc, TH), within groups and / or time points (from baseline through to 39 weeks) not described in the primary or secondary endpoints may be presented

in the exploratory endpoints including:

- EuroQoL (EQ-5D)
- WOMAC Pain Score (100mm VAS)
- OMERACT-OARSI
- Total WOMAC
- WOMAC Stiffness Score
- WOMAC Physical Function Score
- Patient Global Assessment
- Evaluator Global Assessment
- Range of Motion
- Rescue Medication Usage: Difference in analgesic use measured by number of pills taken between visits will be compared between treatment groups descriptively.
- Number of Subjects Considered Treatment Failures: Treatment Failure: A subject who undergoes a procedure or uses a medication (other than the rescue medication) for the treatment of OA in the index knee at any time after the study injection through the 39 week visit.

For the exploratory analyses, the continuous variables will be analyzed via an analysis of variance and contrasts used to assess the prescribed comparisons. For the discrete variables, a Fisher's exact test will be used to assess the desired comparisons.

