4.1.4 Exploratory Endpoints

Any comparisons between groups (Cingal, Monovisc, TH), within groups and / or time points (from baseline through to 39 weeks) not described in the primary or secondary endpoints may be presented in the exploratory endpoints including:

- EuroQoL (EQ-5D)
- WOMAC Pain Score (100mm VAS)
- OMERACT-OARSI
- Total WOMAC
- WOMAC Stiffness Score
- WOMAC Physical Function Score
- Patient Global Assessment
- Evaluator Global Assessment
- Range of Motion
- Rescue Medication Usage: Difference in analgesic use measured by number of pills taken between visits will be compared between treatment groups descriptively.
- Number of Subjects Considered Treatment Failures: Treatment Failure: A subject who undergoes a procedure or uses a medication (other than the rescue medication) for the treatment of OA in the index knee at any time after the study injection through the 12 week visit.

For the exploratory analyses, the continuous variables will be analyzed via an analysis of variance and contrasts used to assess the prescribed comparisons. For the discrete variables, a Fisher's exact test will be used to assess the desired comparisons.

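### Treatment failures through week 39 are compared as a simple count although observation after week 26 is optional and the SAP stops the window at week 12: a low-severity, cheaply repaired weakness in an exploratory endpoint

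*Protocol*

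**What the plan says.** - Protocol 7.3 includes "Number of Treatment Failures due to Additional Procedure or Use of Disallowed Medication" among exploratory endpoints that may, not must, be presented.
- Protocol section 2 (Definitions) and 12.1.3 define a failure as a procedure, or a medication other than rescue, used "for the treatment of OA in the index knee at any time after the study injection through the 39 week visit".
- SAP 4.1.4 gives the same definition with a different end: "OA in the index knee at any time after the study injection through the 12 week visit".
- Protocol 12.1.3 fixes the test: "For the discrete variables, a Fisher's exact test will be used to assess the desired comparisons". SAP 4.1.4 says the same.
- The Protocol synopsis says that eligible subjects who completed week 26 of Cingal 16-02 "will have the option to participate in the sub-study". Protocol 10.2.1 asks for a new consent before the week 39 visit.
- Protocol 12.5 names ITT for the primary and secondary endpoints only, and restricts imputation to WOMAC pain, WOMAC function and the Patient Global Assessment. Neither document states a denominator for treatment failures or a rule for weeks that were not observed.
- Protocol 10.2.12.3 lists the medication data collected: "medication name, dose, unit, route, frequency, start date, stop date, indication". No equivalent list with dates is given for procedures.

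**The concern.** A treatment failure is an event that can occur on any day from injection to week 39. A yes/no count gives the week-39 risk directly only if everyone is watched to week 39. Here, subjects who leave 16-02 early or do not join the extension are unobserved for 13 weeks or more.

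The plan leaves open two ways to count. With all treated subjects as denominator, unobserved weeks are in effect failure-free. With extension participants only, a subject who failed before week 26 and did not continue disappears from numerator and denominator. Either can understate failure. The Cingal–TH contrast can shift if entry differs between arms or depends on having already failed. As written, the choice would be made when the table is programmed. The two windows, 39 and 12 weeks, add a prior ambiguity: under the SAP's window the optional period plays no part.

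**Working it through.** **Plan's own figure.** The documents give no failure rate, entry rate or power for this endpoint. The nearest stated figure is the 16-02 sample size (10 mm, SD 20, 90% power, two-sided 5%, 2:1): n(TH) = (1 + 1/2) × (1.960 + 1.282)² × (20/10)² = 63.04, rounded up to 64, with 128 Cingal. It reproduces. Enrolled arms are 256 Cingal, 256 Monovisc and 64 TH, total 576.

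**Assumptions.** Constant hazard; p is the true 39-week failure proportion; q is the share of subjects failure-free at week 26 who enter the extension. All values of p and q below are assumed.

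- Failure by week t: F(t) = 1 − (1 − p)^(t/39)
- All-treated observed proportion: O = F(26) + q × (p − F(26))

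**1. Equal entry, unrelated to failure (TH 20%, Cingal 10%, q = 0.75).**
- F(26): TH 1 − 0.80^(2/3) = 0.138; Cingal 1 − 0.90^(2/3) = 0.068.
- O: TH 0.138 + 0.75 × 0.062 = 0.185; Cingal 0.068 + 0.75 × 0.032 = 0.092.
- Difference 9.3 points instead of 10.0; the risk ratio stays at 0.50. Exact Fisher power goes from 52.5% to 49.0% (51.1% at 90% entry, 44.3% at 40%).
- Participants only: the proportion is unbiased and the difference stays 10.0 points. Power falls to 42.2% because the arms shrink to 0.75 × 256 = 192 and 0.75 × 64 = 48.

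**2. Entry that depends on earlier failure.**
- One arm with p = 20%, 70% entry if failure-free and 35% if already failed. All treated: 0.138 + 0.70 × 0.062 = 18%. Participants only: (0.35 × 0.138 + 0.70 × 0.062) / (0.35 × 0.138 + 0.70 × 0.862) = 0.092/0.652 = 14%.
- Extreme case, no early failure enters, rates as in step 1: TH 0.062/0.862 = 7.2%, Cingal 0.032/0.932 = 3.5%. The difference is 3.7 points, with power 17.8%.

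**3. Entry that differs by arm (Cingal 15%, TH 30%).**
- Entry 85% Cingal, 65% TH. All treated: Cingal 0.103 + 0.85 × 0.047 = 0.143; TH 0.212 + 0.65 × 0.088 = 0.269. The difference is 12.6 points instead of 15.0.
- Simulated power: about 63% (Fisher, all treated), 42% (Fisher, participants only, early failures half as likely to enter), 75% (log-rank, non-entrants censored at week 26).
- With everyone followed, simulation gives Fisher 73.2% and log-rank 77.4%. So about 4 of the 12 points between 63% and 75% belong to the test, not to optional observation. With equal 90% entry the gap is again 4 points (71.2% vs 75.2%).
- Entry reversed (65% Cingal, 85% TH): Fisher on all treated has 78% apparent power against 75% for log-rank. The count now overstates the difference, so the issue is bias as well as power.

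**4. No true difference, entry 90% Cingal vs 60% TH.** The all-treated count creates a gap of 1.9 points at 20% failure and 3.3 points at 40%. Fisher rejects in 4.7% and 7.0% of trials (4.1% and 4.3% with equal entry). Log-rank with censoring stays at 4.9% and 5.2%.

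**5. The SAP's window.** By week 12, the step 1 rates become 1 − 0.80^(12/39) = 6.6% and 1 − 0.90^(12/39) = 3.2%. Extension entry is irrelevant, and Fisher power is about 23%.

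**6. Limit of the repair.** Suppose failure-free non-entrants have twice the later hazard (70% entry, true risk 20%). Kaplan-Meier then gives 18.6% and the all-treated count 17.2%. Both understate.

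**The case against.** A reader might infer that the plan scores unobserved weeks as failure-free or discards early failures, and hence that the comparison is biased as it stands. The documents do not say so. Protocol 10.2.1 carries all 16-02 data into 17-02, and Protocol 16.9 keeps subjects with deviations in follow-up. Both point against dropping early failures, though neither makes a subject consent to the extension. What the documents establish is a missing rule, from which bias may follow.

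It is also tempting to say that neither denominator can be right. Step 1 shows otherwise: if entry is unrelated to failure, the participants-only proportion is unbiased. Nor is this the only planned view of supplementary treatment. Rescue use through week 39 is a secondary endpoint (Protocol 7.2), and concomitant medications are tabulated by arm (Protocol 12.3).

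Finally, the endpoint is exploratory, optional to present, outside the testing hierarchy and not powered. Part of the log-rank advantage exists with complete follow-up, and a censored analysis does not recover the lost weeks: in the step 1 setting log-rank power falls from 59.5% to 55.3% at 75% entry. These points stand. They lower the severity but do not remove the gap in the plan.

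**Conclusion.** The point holds at low severity. The Protocol counts an event over 39 weeks when observation is optional for the last 13, states no denominator and no rule for unobserved time, and conflicts with the SAP's 12-week window. Under the 39-week definition the count may understate failure, and the arm comparison may be biased if entry differs by arm or depends on earlier failure. With equal entry unrelated to failure the effect is minor (10.0 to 9.3 points at 75% entry). Larger effects need the unequal or outcome-dependent entry assumed in steps 2 to 4. Every failure and entry rate here is an assumption, so neither the direction nor the size of any bias in this trial can be stated from the documents.

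**What to change.** - Reconcile the week-12 and week-39 windows between SAP 4.1.4 and Protocol section 2 and 12.1.3 before choosing an estimator.
- For the 39-week endpoint, analyse time from injection to first treatment failure in all treated subjects, censored at the last assessment. Report Kaplan-Meier failure proportions at weeks 26 and 39 by arm, and compare Cingal with TH by log-rank test.
- Report extension entry by arm and by failure status before week 26.
- Keep the raw count as a descriptive line, together with the count for weeks 0 to 26, which does not depend on extension entry.
- Confirm that the eCRF captures procedure dates, since Protocol 10.2.12.3 lists dates for medications only.

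The cost is SAP and Protocol wording and a short program. No additional patients are needed, and no new data if procedure dates are already recorded. The downside is that censoring at week 26 assumes entry is non-informative among subjects who have not yet failed, so Kaplan-Meier reduces the bias but may not remove it. The entry table lets a reader judge that.

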8 STUDY DESIGN

8.1 Diagram

8.2 Trial Design

This sub-study is an extension of the ongoing Cingal 16-02 trial which is a multi-center, randomized, double-blind, parallel group, active comparator controlled trial to evaluate the efficacy and safety of a single injection of Cingal for the relief of joint pain in subjects with OA of the knee.

Subjects with OA defined as Kellgren-Lawrence (K-L) I-III in the index knee were eligible for this study [9, 10]. Felson et al 2004, encouraged the use of both OA symptoms and radiographic changes in the assessment of OA [11]. Cingal 16-02 study employed both methods to screen subjects. Structural severity was evaluated with the K-L classification score, a composite index of the presence and severity of joint space narrowing, osteophytes, sclerosis, deformity and cysts (see Appendix 4) [9, 10].

For the evaluation of symptomatic severity, two main domains are important [12]. The first is pain and the second is functional impairment. Other domains often used include subject's overall assessment, ROM and performance. Domains identified by OMERACT as core variables to be used in clinical trials involving OA are pain, function and the Patient Global Assessment which were captured as part of the Cingal 16-02 study [12].

Baseline and post-treatment pain, physical function and stiffness is measured using the WOMAC questionnaire in the Cingal 16-02 up to 26 weeks and then to 39 weeks within the Cingal 17-02 trial. Range of Motion, Patient and Evaluator Global Assessment and the EuroQol are used to assess symptomatic severity throughout both studies. In addition, the number of acetaminophen/paracetamol pills taken is captured as an indirect measure of pain and will be done at each visit.

Subjects meeting the inclusion/exclusion criteria for Cingal 16-02 will have been randomized to receive a single injection of Cingal, Monovisc or triamcinolone hexacetonide (TH) in the index knee. Since there is a difference in volume between Cingal, Monovisc and TH, the treating physician is not considered blinded. To maintain the double-blind design of the study, there is a person assigned to the role of Treating Physician and one person assigned to the role of Blinded Evaluator. The Treating Physician, most often the PI, will administer the injection but will not participate in the evaluation of study treatment effectiveness. A second individual, designated as the Blinded Evaluator, is blinded to treatment and will complete the pre- and post-treatment Evaluator Global Assessment, knee exams and ROM measurements. To maintain the subject blinding, the injection syringe will have been prepared separate from the patient and the injection will be masked from the subject. The blinding of the patient and the blinded evaluator will be maintained in both the Cingal 16-02 and Cingal 17-02 trials.

The subject will have been trained on how to complete the WOMAC, Patient Global Assessment and

EuroQol within the Cingal 16-02 trial. The subject should complete these questionnaires prior to any physical evaluation that must be done at the 39 week follow-up visit.

The Blinded Evaluator will collect and record AEs from the subjects and consult the Treating Physician only as needed in the management of AEs. The Blinded Evaluator will be a physician, research nurse, registered physiotherapist or physician assistant trained to perform the assessments outlined in the protocol (Section, 10.1 Schedule of Events).

Up to 40 sites in Europe are participating in the study to enroll 576 subjects. Subject participation in this extension study will last approximately 13 additional weeks beyond the Cingal 16-02 trial with follow-up the visit scheduled at weeks 39 after the treatment injection in Cingal 16-02.

